## **11. Management and Reporting of Adverse Events/Serious Adverse Events/Adverse Events of Special Interest**

### **11.1. Sponsor Review of Safety Information**

Safety information will be collected, reviewed, and evaluated by the Sponsor or designee.

### **11.2. Regulatory Requirements**

The Sponsor or designee is responsible for regulatory submissions and reporting of AEs, SAEs, AESIs per the ICH guidelines E2A and ICH GCP. Country specific regulatory requirements will be followed in accordance with local country regulations and guidelines.

Institutional Review Boards (IRBs)/IECs will be notified of any SAE according to applicable regulations.

In addition to the investigator's assessment of relatedness, the Sponsor or designee will evaluate the available information and perform an independent assessment of all reported SAEs, AESIs, and determine if there is a reasonable possibility that TEGSEDI is causally related to a reported SAE. While the Sponsor may upgrade an investigator's decision, it is not permissible to downgrade the investigator's opinion for the purposes of determining whether the SAE meets the criteria of an Expedited Report.

The Reference Safety Information for this study will be the USPI, CPM or the respective country label as applicable.

### **11.3. Definitions**

#### **11.3.1. Adverse Event**

An AE can be any unfavorable and unintended sign (including an abnormal laboratory finding, for example), symptom, or disease temporally associated with the use of medicinal product, whether or not the AE is considered related to the medicinal product.

An AE can therefore be any of the following:

- Any unfavorable and unintended sign (including an abnormal laboratory finding), symptom, or disease temporally associated with the use of a medicinal product, whether or not considered related to the medicinal product
- Any new disease or exacerbation of an existing disease (a worsening in the character, frequency, or severity of a known condition)
- Recurrence of an intermittent medical condition (e.g., headache) not present at baseline
- Any deterioration in a laboratory value or other clinical test (e.g., electrocardiogram, X-ray) that is associated with symptoms or leads to a change in study treatment or concomitant treatment or discontinuation from TEGSEDI
- AEs that are related to a protocol-mandated intervention, including those that occur prior to assignment of study treatment (e.g., screening invasive procedures such as biopsies)

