### **9.6.4. Safety Analysis**

Patient incidence rates of all AEs will be tabulated by Medical Dictionary for Regulatory Activities (MedDRA) system organ class (SOC), and by MedDRA preferred term (PT). Narratives of deaths, all discontinuations, serious AEs, pregnancies and AEs of special interest (AESI) will also be provided.

All treatment emergent AEs, all treatment emergent AEs potentially related to TEGSEDI, all treatment emergent serious AEs, and all treatment emergent serious AEs potentially related to TEGSEDI will be summarized.

Incidence (95% confidence interval) of AEs occurring within 1 day of TEGSEDI administration, and time to onset from TEGSEDI injection and duration of these AEs will be summarized by visit and overall in any visit. The rates of AEs during the 1-day visit occurring after preventive measures will also be summarized. Resolution time with and without treatment administered for the AEs will be summarized.

For each study visit on treatment, the result and change from pre-dose baseline in vital signs (body temperature, heart rate, respiratory rate, and systolic, diastolic blood pressure) and cytokines/inflammatory markers will be summarized using descriptive statistics for all patients in the Evaluable Set and by presence/absence of AEs within 1 day of TEGSEDI administration.

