## 11.5. Procedures for Handling Special Situations

### 11.5.1. Abnormalities of Laboratory Tests

Clinically significant abnormal laboratory test results may, in the opinion of the investigator, constitute or be associated with an AE. Examples of these include abnormal laboratory results that are associated with symptoms, or require treatment, e.g., bleeding due to thrombocytopenia, tetany due to hypocalcemia, or cardiac arrhythmias due to hyperkalemia. Whenever possible, the underlying diagnosis should be listed in preference to abnormal laboratory values as AEs. Clinically significant abnormalities will be monitored by the investigator until the parameter returns to its baseline value or until agreement is reached between the investigator and Sponsor. Laboratory abnormalities deemed not clinically significant (NCS) by the investigator should not be reported as AEs. Similarly, laboratory abnormalities reported as AEs by the investigator should not be deemed NCS.

The investigator is responsible for reviewing all laboratory reports. The clinical laboratory reports will serve as source documents and should include the investigator's assessment of clinical significance of out of range/abnormal laboratory values. If the lab results are electronically received, the investigator should assess clinical significance and document the assessment in the patient medical record.

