### 8.2.2.2 Adverse Events Occurring Within 24 hours of TEGSEDI Administration

AEs occurring within 24 hours of administration of TEGSEDI are defined as all AEs with an onset date/time no longer than the 24-hour planned timepoint using a window interval from 20 to 30 hours after the date/time of the injection. For AEs with missing time of onset, AEs occurring within 24 hours of TEGSEDI administration are defined as AEs with an onset date of the same day as the TEGSEDI administration or the subsequent day. This rule will also be applied for missing time of administration of TEGSEDI.

The incidence of AEs occurring within 24 hours post TEGSEDI administration will be summarized at each visit and overall using counts and percentages in the evaluable set. The incidence will be reported with 95% confidence intervals (CIs). Additionally, a summary of AEs occurring within 24 hours post TEGSEDI administration will be displayed by SOC and PT and will be summarized at each visit and overall.

The denominator for the calculation of the percentages by visit will be the number of patients who received a TEGSEDI administration for the specific visit. The denominator for the calculation of the percentages for the overall occurrence of AEs in any visit will be the number of patients in the evaluable set. These denominators will also be presented in the table.

The time from the injection of TEGSEDI until the occurrence of the first AE will be summarized by each visit and overall using descriptive statistics for continuous variables. The time (hours) will be calculated as:

(Onset date/time of the AE – injection date/time of TEGSEDI)/3600

Time from injection of TEGSEDI until the onset of the AE will only be summarized for the AEs with available time for the onset of the AE and available time of TEGSEDI injection. Where time is not available, the AE will be included in the incidence count but will not be included in the summary of time to onset.

The duration of AEs occurring within 24 hours of TEGSEDI administration (in hours) will be calculated as:

- $(\text{Date/time of resolution} - \text{date/time of onset})/3600$

Duration of the AEs will only be calculated for AEs with an outcome of "Recovered" or "Recovered with sequelae" for which date/time for onset and resolution is available.

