### 8.2.3 Vital Signs

Vital signs include body temperature, heart rate, respiratory rate, and systolic/diastolic blood pressure, and will be summarized using the evaluable set. Observed values and changes from the pre-injection assessment will be calculated for all assessments. Observed values and changes from the pre-injection value will also be calculated by presence/absence of AEs occurring within 24 hours of TEGSEDI administration. For the treatment period, changes will be calculated based on the pre-treatment value of the specific visit. For the post-treatment follow-up period and the early termination visit, changes will be calculated relative to the pre-treatment assessment at Month 0.

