#### 8.2.4 Cytokines and Inflammatory Markers

Cytokines and inflammatory markers include the following parameters: Immunoglobulin (Ig) E, IgG, IgM, C-reactive protein (CRP), Erythrocyte sedimentation rate (ESR), interferon  $\alpha$  (IFN-  $\alpha$ ), IFN- $\beta$ , Chemokines (Macrophage inflammatory protein (MIP)-1a and membrane cofactor protein (MCP)-1), Granulocyte-macrophage colony stimulating factor (GM-CSF), interleukin (IL)-1 $\alpha$ , IL-1 $\beta$ , IL-6, IL-8, IL-12, and Tumor necrosis factor –  $\alpha$  (TNF-  $\alpha$ ). Cytokines and inflammatory markers will be analyzed in the same way as the vital signs using the evaluable set.

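### Vital signs and inflammatory markers are summarised by whether an AE occurred, but an abnormal vital sign (less often a laboratory result) can itself be that AE, so part of any difference can be built in by definition

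*Combined protocol and SAP*

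**What the plan says.** Protocol 11.3.1 includes among AEs "Any unfavorable and unintended sign (including an abnormal laboratory finding), symptom, or disease temporally associated with the use of a medicinal product". Its fourth bullet is narrower: it ties a worsening laboratory value or other test to symptoms or to a change in treatment. Protocol 11.5.1 says "Clinically significant abnormal laboratory test results may, in the opinion of the investigator, constitute or be associated with an AE", but also "Laboratory abnormalities deemed not clinically significant (NCS) by the investigator should not be reported as AEs", and it prefers a diagnosis to a laboratory value as the AE term. No comparable limit is stated for vital signs.

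Vital signs, inflammatory markers and AEs are all assessed at the same post-injection checks at 1, 2, 4, 8 and 20–30 hours (protocol 9.2.2.1.2).

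SAP 8.2.2.2 defines the in-window AEs without exception: they "are defined as all AEs with an onset date/time no longer than the 24-hour planned timepoint", using the 20 to 30 hour window. Protocol 9.6.4 plans summaries of vital signs and markers "by presence/absence of AEs within 1 day of TEGSEDI administration". SAP 8.2.3 lists the parameters ("Vital signs include body temperature, heart rate, respiratory rate, and systolic/diastolic blood pressure, and will be summarized using the evaluable set") and says "Observed values and changes from the pre-injection value will also be calculated by presence/absence of AEs occurring within 24 hours of TEGSEDI administration". SAP 8.2.4 carries this over: "Cytokines and inflammatory markers will be analyzed in the same way as the vital signs using the evaluable set".

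Nothing in the visible text sets aside AEs that consist of the summarised parameter, limits the values to those before AE onset, or plans a second version of the split.

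**The concern.** The grouping variable is partly defined by the outcome. If a temperature rise at a scheduled check is recorded as pyrexia, that injection enters the AE-present rows and leaves the AE-absent rows because of its temperature. The AE-present rows then look more abnormal and the AE-absent rows flatter, even if no other AE has anything to do with temperature.

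This matters because vital-sign change is named in the objective, and vital signs and markers are endpoints. The split is the only planned summary that relates them to AEs: the risk-factor review in SAP 8.2.2.2 covers medical history, baseline characteristics, concomitant medications and ADA status. A reader who sees the two sets of rows side by side may take the gap as evidence that post-injection reactions in general carry a physiological or inflammatory response.

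**Working it through.** **Figures in the plan.** The plan gives none on this point. Its one sample-size figure reproduces (1 − 0.96^75 = 0.953, stated as 95%) and has no bearing here. The documents give no AE rate, SD or recording rule for vital signs, so every input below is an assumption shown over a range.

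**Standardised model.** Let X be a post-injection change in SD units, unrelated to other AEs.
- p is the probability of another AE.
- c is the level above which X may be recorded as an AE.
- q is the probability that it is so recorded.

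With φ the normal density and T(c) = 1 − Φ(c):
- P(AE) = p + (1 − p)·q·T(c)
- E[X | AE] = (1 − p)·q·φ(c) / P(AE)
- E[X | no AE] = −(1 − p)·q·φ(c) / (1 − P(AE))

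Example with p = 0.2, c = 1.645, q = 0.5, so φ = 0.1031 and T = 0.0500:
- P(AE) = 0.2 + 0.8 × 0.5 × 0.0500 = 0.220
- E[X | AE] = 0.0412 / 0.220 = 0.187
- E[X | no AE] = −0.0412 / 0.780 = −0.053
- Difference = 0.24 SD. A simulation of 2,000,000 injections also gives 0.24. Grouping on the other AEs alone gives −0.003.

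Over p = 0.1 to 0.4 and c = 1.645 or 2.0:

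| q | Built-in difference (SD) |
|---|---|
| 0 | 0 |
| 0.1 | 0.01–0.10 |
| 0.25 | 0.03–0.23 |
| 0.5 | 0.07–0.43 |
| 1 | 0.13–0.75 |

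**Temperature illustration.** Simulation assumptions: five exchangeable normal changes per injection, correlation 0.5, mean zero; SD 0.4 or 0.5 °C; other AEs independent of temperature in 10, 20 or 30% of injections; a fever AE is possible when any change reaches 0.8 or 1.0 °C, and is recorded with probability q. Because the five changes are exchangeable, the difference in mean change is also the expected difference at each scheduled time. A per-injection largest rise is not used, because the SAP plans no such statistic.

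| Share of threshold rises recorded | SD 0.4 °C | SD 0.5 °C |
|---|---|---|
| 0 | 0 | 0 |
| 10% | 0.01–0.04 °C | 0.02–0.08 °C |
| 25% | 0.01–0.09 °C | 0.04–0.17 °C |
| 100% | 0.05–0.26 °C | 0.16–0.42 °C |

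One cell by hand (SD 0.5, threshold 1.0, p = 0.30; 8.4% of injections reach the threshold). The difference equals a numerator proportional to q, divided by P(AE)(1 − P(AE)).
- At q = 1: P(AE) = 0.30 + 0.70 × 0.084 = 0.359, the product is 0.230, and the difference 0.160 gives a numerator of 0.0368.
- At q = 0.25: the numerator is 0.0092, P(AE) = 0.30 + 0.70 × 0.25 × 0.084 = 0.315, the product is 0.216, and the difference is 0.0092 / 0.216 = 0.043 °C.

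The AE-absent mean falls by 0.02–0.05 °C (SD 0.4) or 0.06–0.11 °C (SD 0.5) at full recording, and by 0.004–0.024 °C at 25%.

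**How extreme is the top figure?** The 0.42 °C case (SD 0.5, threshold 0.8, p = 0.1, q = 1) implies that random variation alone produces a fever AE in 18% of injections. The share of AE-present injections that are there only because of fever is 0.9 × 0.18 / (0.1 + 0.9 × 0.18) = 0.162 / 0.262 = 62%.

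**The case against.** The strongest reply is that a fever that is an AE ought to appear as fever in the AE-present rows. The objective is to characterise AEs with respect to vital-sign changes, and for that aim the split is right. The SAP plans descriptive summaries only, with no test and no formal contrast, and it also plans the same parameters without the split. All of this stands, and it is why the planned table should stay. It does not help a reader who wants to know about the remaining AEs.

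Three stronger readings are tempting and not supported:
- **A spurious difference is certain.** It is conditional. If no in-window AE is recorded because of a measured value, it is zero, and the upper figures need every threshold rise to be recorded. No rule in the documents says that.
- **Cytokines and CRP are affected as much as vital signs.** Section 11.5.1 bars results judged not clinically significant and prefers the diagnosis, and the fourth bullet of 11.3.1 asks for symptoms or a treatment change. The broad bullet still lets a laboratory result be the AE, and a diagnosis prompted by a value still moves the injection. But the overlap should be rarer, and the temperature illustration says nothing about its size for markers.
- **An error rate or the sample size is compromised.** There is no hypothesis test, and the 75-patient figure does not depend on this split.

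There are also limits of source. The SAP refers to protocol version 3.0, while the AE definition available is from version 2.0, and the mock tables in SAP Appendix B are not visible. The absence of a rule is established only for the visible text.

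**Conclusion.** The point holds in a limited form. Part of any AE-present versus AE-absent difference in SAP 8.2.3 and 8.2.4 can be built in by definition, mainly for vital signs. The overlap exists whether the unit is the injection at a visit, as in protocol 9.6.4 and the SAP, or the patient, as in the protocol abstract.

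The harm is to interpretation: the split describes AEs including these signs, but cannot alone show whether other AEs come with vital-sign or marker changes. Its size cannot be computed from the documents. The 0.01–0.17 °C and 0.05–0.42 °C ranges illustrate temperature under the assumptions listed and no true link; they are not estimates for this study. The remedy uses existing data and is worth adding before database lock.

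**What to change.** Keep the planned split and add to SAP 8.2.3 and 8.2.4:

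> For each parameter with at least one in-window AE that consists of a change in that parameter, the presence/absence summary will be repeated with those AEs not counted for the split. The preferred-term list will be fixed before database lock.

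Examples for the list are pyrexia for temperature, hypotension or hypertension for blood pressure, and increased CRP for CRP.

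Footnote both tables to say that the AE definition overlaps with the parameters, and that the term list may miss some AEs, because protocol 11.4 asks investigators to report signs and symptoms under one diagnosis where possible.

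The cost is SAP wording, a short term list and a few more tables, only for parameters where such AEs occur. No new data are needed. Some injections change group between versions. In particular, an injection whose only AE is pyrexia joins the AE-absent rows in the repeat and raises their temperature if the fever was a real reaction. Neither version replaces the other, so present both.

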### 11.3.2. Adverse Drug Reaction and Unexpected Suspected Adverse Drug Reaction

#### Adverse Drug Reaction (ADR)

In the clinical experience with a new medicinal product or its new usages, particularly as the therapeutic dose(s) may not have been established, ADR is defined as follows:

All noxious and unintended responses to a medicinal product related to any dose should be considered ADRs.

The phrase "responses to a medicinal product" means that a causal relationship between the medicinal product and the AE has been determined by the Sponsor as at least a reasonable possibility, i.e., the relationship cannot be ruled out.

[figure not shown]
### 11.3.3. Serious Adverse Event

A SAE is any AE that in the view of either the investigator or Sponsor, meets any of the following criteria:

- Results in death
- Is life threatening: that is, poses an immediate risk of death at the time of the event  
An AE or suspected adverse reaction is considered "life-threatening" if, in the view of either the investigator or Sponsor, its occurrence places the patient at immediate risk of death. It does not include an AE or suspected adverse reaction that, had it occurred in a more severe form, might have caused death
- Requires inpatient hospitalization or prolongation of existing hospitalization  
Hospitalization is defined as an admission of greater than 24 hours to a medical facility and does not always qualify as an AE
- Results in a persistent or significant incapacity or substantial disruption of the ability to conduct normal life functions
- Results in a congenital anomaly or birth defect in the offspring of the patient (whether the patient is male or female)
- Important medical events that may not result in death, are not life-threatening, or do not require hospitalization may also be considered serious when, based upon appropriate medical judgment, they may jeopardize the patient and may require medical or surgical intervention to prevent one of the outcomes listed in this definition. Examples of such medical events include allergic bronchospasm requiring intensive treatment in an emergency room or at home, blood dyscrasias or convulsions that do not result in inpatient hospitalization, or the development of drug dependency or drug abuse

The terms "severe" and "serious" are not synonymous. Severity refers to the intensity of an AE (e.g., rated as mild, moderate, or severe).

Severity and seriousness need to be independently assessed for each AE recorded on the eCRF.

## **11.4. Monitoring and Recording Adverse Events**

Any pre-existing conditions or signs and/or symptoms present in a patient prior to the start of the study (i.e., before informed consent) should be recorded as Medical History and not recorded as AEs unless the pre-existing condition has worsened during study treatment. The investigator should always group signs and symptoms into a single term that constitutes a single unifying diagnosis if possible. Before a diagnosis is confirmed, all symptoms should be reported as separate AEs.

### **11.4.1. Serious Adverse Events**

In the interest of patient safety, and in order to fulfill regulatory requirements, all SAEs, AESIs, (regardless of their relationship to TEGSEDI) should be reported to the Sponsor or designee within 24 hours of the study center's first knowledge of the event. The collection of SAEs, AESIs, will begin after the patient signs the ICF and stop at the end of the patient's End of Study visit. When the investigator is reporting by telephone, it is important to speak to someone in person versus leaving a message. SAEs should be reported using an electronic SAE submission form whenever possible. In situations where the electronic SAE submission is unavailable, an Initial SAE Form should be completed, and a copy should be faxed or emailed to the Sponsor or designee. The SAE reporting instruction, including the fax number and email address can be found in the study safety form completion guidelines.

Detailed information should be actively sought and included on Follow-Up SAE Forms as soon as additional information becomes available. All SAEs will be followed until resolution. SAEs that remain ongoing past the patient's last protocol-specified visit will be evaluated by the investigator and Sponsor. If the investigator and Sponsor agree the patient's condition is unlikely to resolve, the investigator and Sponsor will determine the follow-up requirement.

#### 11.4.2. Non-Serious Adverse Events

The recording of non-serious AEs will begin after the patient signs the ICF and will stop at the end of the patient's end-of-study visit. The investigator will monitor each patient closely and record all observed or volunteered AEs (Serious and Non-Serious) on the AE eCRF within 24 hours.

#### 11.4.3. Evaluation of Adverse Events (Serious and Non-Serious)

The investigator's opinion of the following should be documented on the AE eCRF:

##### 11.4.3.1. Relationship to TEGSEDI

The event's relationship to TEGSEDI is characterized by one of the following:

- **Related:** There is clear evidence that the event is related to the use of TEGSEDI, e.g., confirmation by positive re-challenge test
- **Possible:** The event cannot be explained by the patient's medical condition, concomitant therapy, or other causes, and there is a plausible temporal relationship between the event and TEGSEDI administration
- **Unlikely/Remote:** An event for which an alternative explanation is more likely (e.g., concomitant medications or ongoing medical conditions) or the temporal relationship to TEGSEDI administration and/or exposure suggests that a causal relationship is unlikely (For reporting purposes, Unlikely/Remote will be grouped together with Not Related)
- **Not Related:** The event can be readily explained by the patient's underlying medical condition, concomitant therapy, or other causes, and therefore, the investigator believes no relationship exists between the event and TEGSEDI

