## 8.2.2 Adverse Events

### 8.2.2.1 Treatment-emergent Adverse Events (TEAEs)

TEAEs are defined as AEs with an onset date/time on or after the date/time of the first on study administration of TEGSEDI. Related TEAEs are TEAEs with a reported relationship of "Possible" or "Related". TEAEs with a missing relationship will also be counted as Related. Serious Adverse Events (SAEs) will be indicated as such in the eCRF and can be defined as treatment emergent, based on when the SAE initiated. AEs will be summarized using the safety set for the treatment period among both patients who develop a hypersensitivity reaction and those patients who do not develop a hypersensitivity reaction.

TEAEs will be summarized as follows:

- Overview of Treatment-emergent AEs
- Treatment-emergent AEs by System Organ Class and Preferred Term
- Treatment-emergent AEs by System Organ Class, Preferred Term and Severity
- Treatment-emergent AEs Related to TEGSEDI by System Organ Class and Preferred Term
- Treatment-emergent AEs Related to TEGSEDI by System Organ Class, Preferred Term and Severity
- Treatment-emergent Adverse Events of Special Interest (AESI) by System Organ Class and Preferred Term

 	
Title: Statistical Analysis Plan
 
Program Name: "A Phase 4 Safety Study Assessing the Adverse Events Occurring Within 24 Hours of TEGSEDI Administration in Patients with polyneuropathy of Hereditary Transthyretin-mediated Amyloidosis (hATTR-PN)"
 
Protocol #: TEG4004
 
[REDACTED]
 
Version: Final 2.0 Effective Date: 06 October 2023

--	---

- Treatment-emergent AESIs by System Organ Class, Preferred Term and Severity
- Treatment-emergent Serious AEs by System Organ Class and Preferred Term
- Treatment-emergent Serious AEs Related to TEGSEDI by System Organ Class and Preferred Term
- Treatment-emergent AEs leading to discontinuation of TEGSEDI by System Organ Class and Preferred Term

AEs will also be presented in data listings as follows:

- Listing of All Adverse Events
- Listing of Adverse Events Leading to Discontinuation
- Listing of Serious Adverse Events
- Listing of Adverse Events of Special Interest

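### The four causality ratings leave no place for a plausibly timed AE whose alternative explanation is no more likely than TEGSEDI, so related-AE tables may be understated and vary by site

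*Combined protocol and SAP*

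**What the plan says.** Protocol section 11.4.3 asks for the investigator's opinion on the AE eCRF, and 11.4.3.1 requires one of four ratings:

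- *Related* calls for clear evidence of causation, with a positive re-challenge as the example given.
- *Possible* has two conditions joined by *and*, as follows: "The event cannot be explained by the patient's medical condition, concomitant therapy, or other causes, and there is a plausible temporal relationship" to TEGSEDI dosing.
- *Unlikely/Remote*: "An event for which an alternative explanation is more likely", or "the temporal relationship to TEGSEDI administration and/or exposure suggests that a causal relationship is unlikely".
- *Not Related*: another cause readily accounts for the event and the investigator therefore believes there is no relationship.

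The same section adds: "For reporting purposes, Unlikely/Remote will be grouped together with Not Related".

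SAP section 8.2.2.1 turns these ratings into outputs. "Related TEAEs are TEAEs with a reported relationship of" *Possible* or *Related*, and a missing rating also counts as related. Three tables in that section use the rule: related TEAEs, related TEAEs by severity, and related serious TEAEs. SAP section 9 carries a related-TEAE table into the annual progress report.

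Protocol section 11.3.2 describes an adverse drug reaction through a sponsor determination of "at least a reasonable possibility, i.e., the relationship cannot be ruled out".

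**The concern.** A scale from which one rating must be chosen should cover every event. Here *Possible* is closed as soon as another cause can explain the event, while *Unlikely/Remote* opens only when that other cause is more likely. The band between them, where the event could be drug or something else, has no rating. That is the band in which clinicians ordinarily use the word *possible*.

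The study has no control arm and the SAP is descriptive only, so investigator attribution is the main planned way of separating drug effects from disease. The protocol's background section describes involvement of nerves, heart, gastrointestinal tract and other organs, so a competing explanation will sometimes be available. Preventive medication taken before the injection can supply another. If sites resolve the gap differently, the related counts will partly reflect how each site read the definition.

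**Working it through.** The plan states no figure on this point, so the check is to apply the four definitions to every combination of timing and strength of the alternative explanation. All rows below are events without clear evidence of causation; events with it go to *Related*.

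| Timing | Alternative explanation | Rating whose definition is met |
|---|---|---|
| Plausible | None | Possible |
| Plausible | Exists, less likely than TEGSEDI | **None** |
| Plausible | Exists, equally likely | **None** |
| Plausible | Exists, more likely | Unlikely/Remote |
| Plausible | Readily explains the event, and investigator believes no relationship | Unlikely/Remote or Not Related |
| Implausible | Any of the above | Unlikely/Remote (also Not Related in the last case) |

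The gap is two rows. In both, *Possible* fails its first condition because another cause can explain the event. *Unlikely/Remote* fails both of its limbs, since the alternative is not more likely and the timing fits. *Not Related* fails because the investigator does not believe that a relationship is absent.

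Next, the route to the outputs. If an event in the gap is rated *Possible* or left blank, the SAP counts it as related. If it is rated *Unlikely/Remote* or *Not Related*, it leaves the four tables named above.

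Size. Take all AEs that would count as related if an alternative no more likely than TEGSEDI did not bar *Possible*. Let s be the share of these that fall in the gap, and d the share of gap events rated down. The related count then falls by s × d. The documents give neither quantity. Assumed values for illustration:

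- s = 10%: fall of 0% (d = 0) to 10% (d = 1)
- s = 30%: fall of 0% to 30%
- s = 50%: fall of 0% to 50%

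The upper ends only restate the assumed s. They bound the effect and do not estimate it.

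Finally, the outputs that do not depend on causality. SAP section 8.2.2.2 defines the 24-hour endpoint over all AEs. The all-TEAE, AESI and all-serious-AE tables in 8.2.2.1 also make no use of the rating.

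**The case against.** Four counter-arguments deserve an answer.

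**Most events do have a rating.** A reader might infer that any well-timed AE with another explanation is stranded. The documents do not support that: a more likely alternative fits *Unlikely/Remote*, and a ready explanation with a belief in no relationship fits *Not Related*. Only the equally-or-less-likely band is uncovered.

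**The direction is not fixed.** A reader might infer that a literal site must rate gap events as not related. It need not, because the same literal reading bars those ratings too. Section 11.4.3 asks for an opinion, an investigator may well choose *Possible*, and a blank counts as related. Under-counting is therefore a risk and not a certainty. Inconsistency between sites is also a risk.

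**Section 11.3.2 is not a flat contradiction.** It concerns adverse drug reaction status as determined by the sponsor, whereas 11.4.3.1 is the investigator's eCRF rating. The assessor and the purpose differ. It remains true that the investigator is given the stricter test.

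**The sponsor reviews safety data.** Section 11.2 provides an independent assessment, and the sponsor may upgrade an investigator's decision. That assessment covers SAEs and AESIs, so a non-serious AESI is reviewed as well; other non-serious AEs get no such causality assessment. The SAP builds its tables on the reported relationship and does not say that an upgrade feeds them.

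One caveat stands in full. The protocol supplied is v2.0, while the SAP's introduction cites version 3.0 of 23 May 2023. The current wording of 11.4.3.1, and any clarification in eCRF guidance, cannot be seen.

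**Conclusion.** The point holds in a bounded form. As written in protocol v2.0, the causality scale is not exhaustive: a plausibly timed AE without clear evidence, whose alternative explanation is equally or less likely than TEGSEDI, meets no definition. Such events may be reported as not related and may be rated differently between sites. The exposed outputs are the related-TEAE and related-serious-AE tables and the annual report's related-TEAE table. The exposure is greatest for non-serious AEs that are not AESIs.

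The documents do not allow the number of affected events to be estimated, and no percentage fall in the related count should be quoted as a finding. The main incidence endpoint is untouched. The conclusion assumes that version 3.0 keeps the v2.0 wording. The correction is worth making because it is cheap and the tables concerned are named safety outputs.

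**What to change.** 1. Check whether protocol version 3.0 keeps this definition of *Possible*. If it does not, the point falls away for ratings made under that version.
2. If it does, reword *Possible* to: *There is a plausible temporal relationship and a reasonable possibility that TEGSEDI caused the event; another explanation may exist but is not more likely.* Both empty rows of the table then fall under *Possible*, and the boundary with *Unlikely/Remote* is closed. This moves closer to section 11.3.2 without fully matching it, because a relationship can remain impossible to rule out even when another cause is more likely.
3. Leave the SAP grouping of *Possible*, *Related* and missing unchanged.
4. Flag in the report which ratings were made before and after the change. If ratings are already complete, do not change the definition; state the one used and that related counts may be understated.

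Cost: one sentence in the protocol and in the eCRF completion guidance, and a notice to sites. The downside is that slightly more AEs will be reported as related, and ratings before and after the change will not be fully comparable.
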